2.2. Background

Disease state

UC is a chronic relapsing and remitting disease characterized by inflammation, ulceration, and bleeding in the colon and rectum. Symptoms include diarrhea; RB; bowel urgency; and tenesmus, a feeling of incomplete evacuation of the rectum after defecation, even though there is no remaining stool to expel. UC has a relapsing remitting course, meaning that many individuals have intermittent disease flares that are interspersed with periods of remission.

Treatment goals

Treatment goals in UC traditionally include induction of remission, typically within a 6- to 12-week time frame, and maintenance of remission in the longer term as assessed over 52 weeks of continuous treatment in clinical studies.

In both clinical practice and clinical studies, clinical response and clinical remission are assessed by a combination of improvement in the endoscopic appearance of the mucosa and healing of ulcers and patient-reported outcomes, including a reduction in SF and a resolution of RB (Levesque et al. 2015). Control of intestinal inflammation in UC is associated with a reduction in corticosteroid use, risk of hospitalization, colectomy and, in the longer term, UC-associated dysplasia and colorectal cancer.

Importance of bowel urgency

More than 80% of individuals with UC experience bowel urgency (Petryszyn et al. 2018; Nóbrega et al. 2018; Newton et al. 2019; Dulai et al. 2020) and 50% experience bowel urgency at least once a day (Petryszyn et al. 2018). More than 40% of individuals experience bowel urgency, even when SF and RB measure scores are 0 (Hibi et al. 2020). An estimated 36% to 54% of individuals with UC report having a deferral time (make it to the bathroom on time) of less than 5 minutes and nearly 18% have less than 2 minutes. In severe cases, individuals have less than 30 seconds to make it to the bathroom. These data demonstrate that bowel urgency has a significant negative impact on the QoL, and the functional ability of individuals with UC.

The American College of Gastroenterology clinical guidelines specifically highlight the need to evaluate urgency of defecation when diagnosing and assessing disease severity, driving a growing need to characterize this endpoint for clinical practice. Regulatory bodies are also interested in defining and validating patient-reported outcomes beyond SF and RB, with bowel urgency being one of the most relevant symptoms to patients (Danese et al. 2019).

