SAP	statistical analysis plan	
SC	subcutaneous	
Screen	The act of determining if an individual meets minimum requirements to become part of a pool of potential candidates for participation in a clinical study	
CCI		
SF	stool frequency	
SMD	standardized mean difference	
SMQ	standardized MedDRA query	
SoA	Schedule of Activities	
SOC	system organ class	
ТВ	tuberculosis	

CONFIDENTIAL

Term	Definition
TBL	total bilirubin level
TEAE	Treatment-emergent adverse event: An untoward medical occurrence that emerges during a defined treatment period, having been absent pretreatment, or worsens relative to the pretreatment state, and does not necessarily have to have a causal relationship with this treatment
TNF	tumor necrosis factor
UC	ulcerative colitis
ULN	upper limit of normal
UNRS	urgency numeric rating scale
CCI	

Version history

This Statistical Analysis Plan (SAP) for study I6T-MC-AMBZ is based on the protocol dated 16FEB2023.

 Table AMBZ.1.0.
 SAP Version History Summary

SAP Version	Approval Date	Change	Rationale
1.0	05APR2023	Not Applicable	Original version
2.0	24APR2024	No Changes	Version updated to reflect yearly review
3.0	21NOV2024	Section 1.2	Added details about the continued access period and continued access follow-up period start and stop details
		Table AMBZ.4.1.	Updated language for period definition to accommodate Continued Access Period.
		Section 4.3.2 Main analytical approach	Added explanation for odds ratio, Youden's index and standardized mean difference methods.
		Table AMBZ4.2	Switched binary and continuous variables in the ANCOVA analysis
		Table AMBZ4.3	Added footnotes to describe confidence interval analysis
		Table AMBZ.4.3 Table AMBZ.6.2.	Updated APU for bowel urgency from bowel urgency measures to QoL measures, adjusted table for APU correlation analysis accordingly.
		4.6.2 Adverse Events	Added additional explanation for TEAE definition. Updated language that some safety analysis listings may be provided as appropriate.
		4.6.7 Concomitant Therapy/ Procedure	Updated procedures from 'will be summarized' to 'may be summarized.'
		Section 4.5.1	Added CCI to analysis.
		Table AMBZ.6.1.	Updated language for description and definition of
		Table AMBZ.6.3	Removed CCI from options on the prior therapy eCRF for biologic agents in footnote.

CONFIDENTIAL

		Updated definition of location of disease
		Added a footnote for definition of S1P.
		Added prior advanced therapy exposure and prior advanced and biologic therapy failure.

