1.2. Study Design

This is a multicenter, open-label, single-arm Phase 3b study to investigate bowel urgency and its relationship with other outcome measures in participants with moderately to severely active UC treated with mirikizumab over a colored week period.

Design

The study will have 4 study periods:

Period I (days)

Participants must complete all Visit 1 screening activities within days prior to Visit 2. The screening endoscopy must occur within days prior to Visit 2.

Period II (weeks)
Participants will receive CCI mg mirikizumab CCI
Period III (weeks)
Participants will receive CCI mg mirikizumab CCI

Note: Participants planning to participate in continued access must complete self-administration training during at least 2 visits between Visits 6 and 9 (see Section 6.1.1 of protocol). Upon completion of all Visit 10 activities, eligible participants may enter the Continued Access Period.

Period IV

Participants who meet the following criteria should enter posttreatment follow-up, including completion of Visit 801:

Continued Access Period (CAP)

Participants who successfully completed Visit 10 and are eligible to enter the CAP. Participants will enter the CAP on the same day that they complete Visit 10 and remain until they discontinue from treatment in the CAP portion of the study. The CAP period will begin at dose of Visit 501 minus 1 minute and end at treatment discontinuation visit.

Continued Access Follow-up Period

Participants who entered the CAP and then discontinued treatment will enter the CAP follow-up period. They exit the CAP follow-up period when they complete Visit 901.

See Figure AMBZ.1 in this SAP for schema. The Schedule of Activities (SoA) is described in Section 1.3 of protocol.

CCI

^a Participants who are eligible for continued access should move directly from Visit 10 to Visit 501, on the same day, if possible. Visit 801 should not be performed.

b Optional Continued Access Period is described in Section 10.12 of the protocol.

2. Statistical Hypotheses

The primary objective is to assess the improvement from baseline in UNRS in participants treated with mirikizumab at Week. No formal hypothesis testing will be performed on the primary endpoint.

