4.4.2. Main Analytical Approach

The analysis of the secondary endpoints is described in Table AMBZ.6.2. Descriptive summaries and CI will be provided for continuous and binary secondary endpoints as indicated in Section 4.1.1.

Analysis of association between secondary endpoints is described in Table AMBZ.4.2 and Table AMBZ.4.3. At Week or Week these analyses will be performed among participants with available data that do not discontinue prior to the time point of interest.

Table AMBZ.4.2. Type of Endpoints and Association Analyses

[figure not shown]
Dependent Outcome	Explanatory Outcome	Analysis
Continuous	Continuous	
Continuous	Binary	UUI
Binary	Binary	

Abbreviations: COl Youden's index (Youden 1950) (Kadel 2012); YI =

Table AMBZ.4.3. Type of Assessments and Endpoints for Association Analyses

Assessments	Endpoint Type	Endpoint	
Bowel Urgency	Continuous	UNRS, BUF, SDT, CCI	
Assessments			
	Binary	UNRS CMI, UNRS Remission	
QoL/Function Measures	Continuous	CCI	
	Binary	CCI	
Symptom/ Symptom Severity of UC	Continuous	CCI	
	Binary	CCI	
Histological Features	Continuous	(Analysis value, and CFB if applicable)	

Assessments	Endpoint Type	Endpoint
	Binary	
Additional Exploratory Measures	Continuous	

The odds ratio (OR) is calculated using logistic regression with 95% Wald confidence intervals, as implemented in SAS PROC LOGISTIC.

The Youden's Index (YI) and corresponding 95% confidence intervals are calculated using the equations presented in Youden, W.J. (1950).

The standardized mean difference (SMD) is calculated by mean difference divided by pooled standard deviation, where pooled standard deviation is obtained by taking the square root of the weighted average of the variances of each group in binary outcome, where the weights are the degrees of freedom of each group.

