4.9 Changes to Protocol-Planned Analyses

There are no changes to the analyses described in the protocol.

5. Sample Size Determination

Approximately 160 participants will be assigned to study intervention. The sample size was determined by considering the precision of the estimated correlation between endpoints. Simulations were performed for both binary and continuous measures where the true correlation varied between CCI . The average half width of the 95% CI for the correlations at Week varied between under considered assumptions for an overall sample size of 160. The average half width of the 95% CI varied between for endpoints during the maintenance period under the assumption that CCI of participants could discontinue early from the study.

Additionally, the proposed sample size of 160 participants is considered sufficient to have power to detect a significant (non-zero) change from baseline in UNRS at Week (primary endpoint).

6. Supporting Documentation

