		OR, YI with CCI remission OR, YI with CCI response			
IIC Compton /C	symptom Severity Analy				
oc symptom/S	symptom Severity Analy	7515			
CCI	CCI	Descriptive summaries,	FAS	Baseline (if	
		including 95% CI		applicable), CCI	
CCI	CCI	Descriptive summaries,			

Measure	Variable	Analysis Method	Population	Time Point(s)
		including 95% CI		
Absolute SF	Absolute SF Score	Descriptive summaries,		
2.5	~~ .	including 95% CI		
Mayo	SF subscore	Descriptive summaries,		
	RB subscore	including 95% CI Descriptive summaries,	-	
	KD subscore	including 95% CI		
	MMS	Descriptive summaries,		
		including 95% CI		
	Symptomatic	Descriptive summaries,		
	Remission	including 95% CI		
	Clinical Remission	Descriptive summaries,		
	City is all Decreases	including 95% CI	-	
	Clinical Response	Descriptive summaries, including 95% CI		
	Alternate Clinical	Descriptive summaries,	-	
	Remission	including 95% CI		
Mayo	Endoscopic	Descriptive summaries,	FAS	Baseline (if
	Normalization	including 95% CI		applicable), CCI
	Endoscopic	Descriptive summaries,		
E C NDC	Remission	including 95% CI		
Fatigue NRS	Fatigue NRS Score	Descriptive summaries, including 95% CI		
Abdominal	Abdominal Pain	Descriptive summaries,	-	
Pain NRS	NRS Score	including 95% CI		
Nocturnal stool		Descriptive summaries,		
	Score	including 95% CI		
CCI	CCI	Descriptive summaries,		
		including 95% CI		
	CCI	Descriptive summaries,		
		including 95% CI		
Bowel	UNRS, CCI	CCI		
Urgency Analysis		coefficient with CCI		
Allalysis		coefficient with CCI		
		CCI	1	
		coefficient with Mayo SF		
		CCI		
		coefficient with Absolute SF		
		CCI		
		coefficient with Mayo RB	-	
		coefficient with AP NRS		
		CCI	1	
		coefficient with Fatigue NRS		
		Pearson + Spearman correlation		
		coefficient with Nocturnal Stool		
		ANCOVA with clinical response		
		ANCOVA with endoscopic remission	-	
		ANCOVA with endoscopic remission ANCOVA with endoscopic	-	
		normalization		
		ANCOVA with symptomatic	1	

Measure	Variable	Analysis Method	Population	Time Point(s)
		remission		
	CED IDIDG CED	ANCOVA with CC		
	CFB UNRS, CFB	coefficient with CFB CCI		
		CCI		
		coefficient with CFB Mayo SF		
		coefficient with CFB Absolute SF		
		coefficient with CFB Mayo RB		
		coefficient with CFB AP NRS		
		CCI		
		coefficient with CFB Fatigue NRS		
		coefficient with CFB Nocturnal Stool		
		ANCOVA with clinical response		
		ANCOVA with clinical remission		
		ANCOVA with endoscopic remission ANCOVA with endoscopic		
		normalization		

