		ANCOVA with symptomatic		
		remission		
Bowel	CFB UNRS, CFB	ANCOVA with CC	FAS	Baseline (if
Urgency	cci , CFB cci			applicable), CCI
Analysis				
	UNRS CMI, UNRS	ANCOVA with CFB CC		
	Remission	ANCOVA with CFB Mayo SF		
		ANCOVA with CFB Absolute SF		
		ANCOVA with CFB Mayo RB		
		ANCOVA with CFB AP NRS		
		ANCOVA with CFB Fatigue NRS		
		ANCOVA with CFB Nocturnal Stool		
		OR, YI with clinical response		
		OR, YI with clinical remission		
		OR, YI with endoscopic remission		
		OR, YI with endoscopic normalization		
		OR, YI with symptomatic remission		
		OR, YI with Bristol Loose Stool		
Exploratory Ana	alyses	1 - ,		l .
		Descriptive summaries, including 95%CI	FAS	Baseline (if applicable), CCI
		Descriptive summaries, including 95% CI		11 77
		Descriptive summaries, including 95% CI		
		Descriptive summaries, including 95% CI		
		Descriptive summaries, including		
		95% CI Descriptive summaries, including		
		Descriptive summaries, including		!

Measure	Variable	Analysis Method	Population	Time Point(s)
		95% CI		(-)
		Descriptive summaries, including 95% CI		
		Descriptive summaries, including 95% CI		
		Descriptive summaries, including 95% CI		
		Descriptive summaries, including 95% CI		
		Descriptive summaries, including 95% CI		
		Descriptive summaries, including 95% CI		
		Descriptive summaries, including 95% CI		
Bowel Urgency	UNRS, CCI	coefficient with CCI		
Analysis		coefficient with CCI		
		coefficient with WIS	_	
		coefficient with SAA		
		ANCOVA with CCI		
Bowel	UNRS, CCI	ANCOVA with CCI	FAS	Baseline (if
Urgency Analysis		ANCOVA with CCI		applicable), CCI
		ANCOVA with CCI		
		ANCOVA with CCI		
		AIVEOVA WILLI		
		ANCOVA with CCI		
		coefficient with CCI		
		coefficient with CCI		
	CFB UNRS, CFB	coefficient with CFB CCI		
		coefficient with CFB CCI		
		CCI coefficient with CCI		
		coefficient with CCI CFB		
	UNRS CMI, UNRS Remission	OR, YI with CCI		
	Kemission	OR, YI with CC	_	
		OR, YI with CCI	_	
		, 11 mm		

Measure	Variable	Analysis Method	Population	Time Point(s)
		OR, YI with CCI		
		OR, YI with CCI		
		OR, YI with CCI		
	UNRS CMI, UNRS	ANCOVACCI		
	Remission,	ANCOVA with CC CFB		
		ANCOVA with CC		
		ANCOVA with CCI CFB		

Additional exploratory analysis will be performed as appropriate.

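### Does the odds-ratio analysis in SAP 4.4.2 need a written rule for a 2x2 table with an empty cell?

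*SAP*

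**What the plan says.** The footnotes to Table AMBZ.4.3 in SAP 4.4.2 give the method: "The odds ratio (OR) is calculated using logistic regression with 95% Wald confidence intervals, as implemented in SAS PROC LOGISTIC". The footnote carries no exception.

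Table AMBZ.6.2 applies it widely. It has 14 legible rows pairing an odds ratio with Youden's index: 2 in the quality-of-life block (such as "OR, YI with CCI remission"), 6 in the symptom block (such as "OR, YI with endoscopic normalization") and 6 in the exploratory block. Each row covers UNRS CMI and UNRS Remission, so there are 14 × 2 = 28 odds ratios per time point.

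On numbers, SAP Section 5 says: "Approximately 160 participants will be assigned to study intervention". SAP 4.4.2 then limits the secondary association analyses: "these analyses will be performed among participants with available data that do not discontinue prior to the time point of interest". So 160 is roughly the ceiling for any table.

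On the role of these results, SAP Section 2 says: "No formal hypothesis testing will be performed on the primary endpoint". SAP 2.1 adds that no multiplicity control applies.

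Some of the text that could hold a fallback cannot be read. The analysis entry for binary against binary in Table AMBZ.4.2 is blank, Section 4.1.4 on missing data is redacted, and Section 4.3.2 ends in a redaction. The version history lists, against Section 4.3.2: "Added explanation for odds ratio, Youden's index and standardized mean difference methods".

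**The concern.** In a 2x2 table with one empty cell, the logistic likelihood keeps rising as the coefficient grows. The fit does not converge, the standard error explodes, and the printed odds ratio depends on where the iterations stop. The specified method then yields nothing to report, and any substitute would be chosen after the data were seen.

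The point deserved a check for three reasons. Association between endpoints is what this study is for, and the precision of correlations set its sample size. Some of the outcomes, endoscopic normalization for instance, may be uncommon. And an empty cell is most likely where an uncommon outcome overlaps almost completely with the urgency endpoint, so the method could fail on the strongest associations. At stake would be the estimate and interval for the affected rows.

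**Working it through.** The plan states no figure for any odds ratio, so there is nothing of its own to reproduce. The check has four steps.

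**1. Does the method fail?** With cells a, b in one row and c, d in the other, OR = ad/(bc) and the standard error of log OR is √(1/a + 1/b + 1/c + 1/d). Both need four non-zero cells.

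- Illustrative table 30/60 and 5/65 (total 160): OR = 30 × 65 / (60 × 5) = 6.50, 95% CI 2.37 to 17.8. The method works.
- Illustrative table 30/60 and 0/70 (total 160): the fitted OR is 246 after 5 iterations, 4,962 after 8 and about 270,000 after 12. By then the interval runs from effectively zero to effectively infinity.

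So it fails, but only for maximum likelihood with a Wald interval. An exact conditional interval for the second table is 8.35 to infinity.

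**2. How likely is an empty cell?** Let p be the prevalence of the outcome, v the share of those with the outcome who meet the urgency endpoint (the overlap), and u the share of those without the outcome who meet it. All three are assumptions. The cell probabilities are pv, p(1 − v), (1 − p)u and (1 − p)(1 − u). The chance of at least one empty cell follows by inclusion-exclusion. At high overlap it is almost entirely the chance that nobody has the outcome without meeting the urgency endpoint, [1 − p(1 − v)]^n. With p = 10%, v = 90%, n = 160 that is 0.99^160 = 20%. With v = 60% it is 0.96^160 = 0.15%.

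Full results for n = 160 and u = 40%; setting u to 20% or 60% does not change them at the precision shown:

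| Prevalence | v = 50% | 60% | 80% | 90% | 95% |
|---|---|---|---|---|---|
| 5% | 3.5% | 4.7% | 20% | 45% | 67% |
| 10% | 0.05% | 0.15% | 4% | 20% | 45% |
| 15% | about 0 | about 0.01% | 0.8% | 9% | 30% |
| 25% | about 0 | about 0 | 0.03% | 2% | 13% |
| 40% | about 0 | about 0 | about 0 | 0.2% | 4% |

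The discontinuation rate is redacted. With an assumed 15% loss, n = 160 × 0.85 = 136, and the 10% row becomes 0.2 / 0.4 / 6 / 25 / 51%.

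**3. Where in the table is this trial likely to sit?** The only related figure is in Protocol 2.2: "More than 40% of individuals experience bowel urgency, even when SF and RB measure scores are 0". If more than 40% of people with no stool-frequency or bleeding symptoms still have urgency, fewer than 100 − 40 = 60% are free of it. For remission-type pairs that points to the columns at 60% or below, where the risk is under 5% even at 5% prevalence and negligible from 10% upward. The figure is background, does not use the UNRS Remission definition and says nothing about UNRS CMI. It is a pointer only.

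**4. What is lost if it happens?** Take 16 participants with the outcome and 144 without, of whom 58 meet the urgency endpoint.

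- 15 of 16 meet it: OR = 15 × 86 / (1 × 58) = 22.2, standard error √(1/15 + 1/1 + 1/58 + 1/86) = 1.047, 95% CI 2.9 to 173. One discordant participant is enough for a finite result.
- 16 of 16 meet it: no planned OR. Firth's penalised fit gives (16.5 × 86.5) / (0.5 × 58.5) = 48.8, profile 95% CI 6.4 to 6267. Only the lower limit is informative.
- Youden's index for the same two tables: 15/16 + 86/144 − 1 = 0.535 and 16/16 + 86/144 − 1 = 0.597. It stays finite.

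Youden's index would also be undefined if nobody had the outcome. At 5% prevalence that chance is 0.95^160, about 0.03%.

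**The case for a change.** The best argument for acting is that it costs almost nothing. One sentence naming a penalised or exact fallback would remove a choice made after seeing the data, in the analyses the study exists to deliver, and tables without an empty cell would be unchanged. The mechanics and the low cost both stand.

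Three things weaken it. First, the post-hoc choice cannot steer a conclusion. The data in such a table are visible at a glance, and Firth, an exact interval or a not-estimable entry with the counts would all tell the reader that the association is strong and its upper limit unknown. Second, no candidate is clearly best. Firth's upper limit can be uninformative, as above, and it mixes penalised with ordinary estimates in one table. In simulation its coverage within empty-cell tables alone was about 70% at 10% prevalence and 80% overlap, partly because such tables are rare there. Selecting a rule is a matter of preference. Third, the absence cannot be established, since the binary-binary entry of Table AMBZ.4.2 and all or part of Sections 4.1.4 and 4.3.2 are unreadable.

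**Conclusion.** No change to the plan is needed. It is true that the stated maximum-likelihood and Wald method gives no usable odds ratio when a cell is empty, and that the legible footnote makes no exception. What is missing is a contingency rule for a case that shows itself in the output and has several acceptable remedies. SAP 4.1 already leaves room for additional exploratory analyses, so an analyst can report the row as not estimable with its four counts and the planned Youden index, adding an exact or penalised interval if wanted.

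The size depends on unknown rates. The risk for a single table is negligible for common or moderately overlapping outcomes. It becomes material only for uncommon outcomes with high overlap: 20% to 45% at 10% prevalence with 90% to 95% overlap, and 20% to 67% at 5% prevalence with 80% to 95% overlap. These figures assume n = 160; with n = 136 they are somewhat higher. In every case the effect is confined to individual descriptive rows. The primary endpoint and the other association measures are untouched.

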4.5. Exploratory Endpoints Analysis

Analysis of the exploratory endpoints other than gene expression endpoints are described in Table AMBZ.6.2. Analysis of associations between exploratory endpoints is described in Table AMBZ.4.2 and AMBZ.4.3.

4.6. Safety Analyses

Safety will be assessed by describing the following: AEs, laboratory analytes, vital signs, and adverse events of special interest (AESIs). Additional analysis will be included if applicable.

4.6.1. Extent of Exposure

Duration of exposure to study treatment will be summarized for the safety population. For the study periods of interest, exposure will be calculated as the time period length in years (see Section 4.1.3) with start and end dates described in Table AMBZ.4.1.

Total participant-years of exposure will be reported by treatment. Descriptive statistics will be provided for participant-weeks of exposure and the frequency of participants falling into different exposure ranges will be summarized. Exposure ranges will generally be reported in weeks using the following as a guide:

- >0 to <4 weeks, ≥ 4 weeks to <8 weeks, ≥ 8 weeks to <12 weeks, ≥ 12 weeks to <16 weeks, ≥ 16 weeks to <20 weeks, ≥ 20 weeks to <24 weeks, ≥ 24 weeks to <28 weeks.
- $>0, \ge 4$ weeks, ≥ 8 weeks, ≥ 12 weeks, ≥ 16 weeks, ≥ 20 weeks, ≥ 24 weeks, ≥ 28 weeks.

Additional exposure ranges may be considered if necessary.

Treatment compliance will be summarized as described in Appendix 4. Interruption of study treatment and the reasons drug not administered will be summarized for injection and infusion separately.

